8.3 Required Concomitant Medications and Procedures

See inclusion criteria (Section 4.2) for a description of PPI medication requirements and corticosteroid treatment requirements for study eligibility. See Section 6.1 for screening EGD requirements.

9 STATISTICAL CONSIDERATIONS

9.1 Overview

This is a Phase 3, multicenter, multinational, randomized, double-blind, placebo-controlled induction and maintenance study to evaluate the efficacy and safety of CC-93538 in adult and adolescent subjects with EoE. The study will incorporate a 24-week Induction Phase followed by

a 24-week Maintenance Phase. Subjects will be randomized according to the following stratification factor: Steroid Inadequate Responders/Intolerant status (yes or no). An independent Data Monitoring Committee (DMC) will be used to review the safety data regularly during the course of the study.

A primary database lock will be performed when all randomized subjects in this study have completed Week 48 of the Maintenance Phase or discontinued the study, including all Safety Follow-up Period data available to date. Analyses in the primary clinical study report (CSR) will be based on this database. The final database lock will be performed at the end of the study including data for any additional subjects who completed the Safety Follow-up Period after the time the last subject completes Week 48 and any updates for adverse events previously ongoing at the time of the primary database lock. The additional data between the primary database lock and last subject completing last visit in this study will be summarized in an addendum to the primary CSR.

Analysis details not explained in the statistical section of the protocol will be provided in the Statistical Analysis Plan (SAP). In addition, the statistical analysis for the EU will be described in the SAP.

9.2 Study Population Definitions

All study populations will be defined and documented prior to database lock. The following analysis populations will be used in the statistical analysis:

Intent-to-treat (ITT) Population

The ITT population will consist of all randomized subjects regardless of whether or not the subject received IP (CC-93538 or placebo).

The ITT population will be used as the primary population for all efficacy parameters. Subjects who prematurely withdraw from the trial for any reason and for whom an assessment is not performed for any reason will still be included in the ITT analyses. Subjects who received incorrect IP from what was randomized will be included in the treatment group according to the intended randomization. Subjects who were randomized with a misreported stratum will be analyzed according to their original (misreported) stratum.

Safety Population

The Safety population will consist of all subjects who received at least one dose of IP. This population will be used for all summaries of safety data. Subjects randomized to placebo who receive any dose of CC-93538 will be summarized in the CC-93538 group. Subjects randomized to CC-93538 who receive only placebo will be summarized in the placebo group; otherwise, they will be summarized in the CC-93538 group.

9.3 Sample Size and Power Considerations

A total sample size of 399 subjects (266 subjects for CC-93538 and 133 subjects for placebo) with a 20% dropout rate at the end of the Induction Phase (212 subjects for CC-93538 and 106 subjects for placebo) will provide at least 90% power to detect a difference of -2.79 change in DD from

baseline at Week 24 and at least 90% power to detect a difference of 15% at Week 24 in histologic response with a two-sided significance level (alpha) of 0.05. These calculations were based on a 2 sample t-test assuming a pooled standard deviation of 4.76 for change in DD from baseline and the chi-square test to compare the difference in 2 independent proportions for the histologic response assuming that the true placebo response proportion is 0.05.

9.4 Background and Demographic Characteristics

Summaries for the demographics, baseline characteristics, medical history, prior medication, and protocol deviations will be presented for the ITT population by treatment for the Induction Phase and by treatment and in Total CC-93538 for the Maintenance Phase. Concomitant medications will be presented for the Safety population by treatment for the Induction Phase, and by treatment and in Total CC-93538 for the Maintenance Phase. Individual listings will also be provided, including concomitant medical procedures for the Safety population.

9.5 Subject Disposition

The disposition of subjects will be summarized with numbers and percentages by treatment for all randomized subjects. Summaries will include the number and percentage of subjects in the following categories:

- Never dosed, dosed, completed the study, permanently discontinued from IP, and discontinuation from the study
- Time to permanent discontinuation from IP and time to discontinuation from the study
- Primary reasons for discontinuation from the study

Subjects in each analysis population as defined in Section 9.2 will be summarized with number and percentage.

9.6 Efficacy Analysis

9.6.1 Efficacy Analysis of the Co-primary Endpoints

9.6.1.1 Overview of Attributes of the Main Estimand for the Co-primary Endpoints

The main estimand of interest for the co-primary endpoints are provided in Table 7 and Table 8.

For intercurrent event (ICE) number 1, the treatment policy estimand strategy will be used where all observed data will be included in the primary analysis regardless of the occurrence of the ICE according to the respective endpoint definition. For ICE number 2, a composite variable estimand strategy will be used where data after rescue therapy or prohibited medication which may impact the efficacy assessment will be set as non-responders for histologic response and worst possible value for change in DD.

Table 7: Summary of Attributes of the Main Estimand for the Co-primary Endpoint - Change in DD from Baseline at Week 24

Estimand Attribute	Definition for Co-primary Endpoint Clinical Response		
Treatment	Randomized treatments with or without use of rescue therapy/prohibited medication		
Population	Adult and adolescent patients with EoE		
Variable	Change in DD from baseline at Week 24		
Intercurrent Events (ICEs)	Event	Strategy	Description/Rationale
	ICE 1: Treatment discontinuation in subjects without the use of concomitant rescue therapy or prohibited medication before the planned 24 weeks	Treatment Policy	Observations post ICE are used to reflect clinical practice
Population-level Summary	ICE 2: The use of concomitant rescue therapy or prohibited medication which may impact the efficacy assessment for CC-93538, regardless of treatment discontinuation, before the planned 24 weeks	Composite Variable	Data post ICE will be set as worst possible value to reflect treatment failure
	Difference in mean changes between treatment groups		

Table 8: Summary of Attributes of the Main Estimand for the Co-primary Endpoint - Histologic Response at Week 24

Estimand Attribute	Definition for Co-primary Endpoint Histologic Response		
Treatment	Randomized treatments with or without use of rescue therapy/prohibited medication		
Population	Adult and adolescent patients with EoE		
Variable	Peak esophageal eosinophil count \leq 6 eos/hpf at Week 24		
Intercurrent Events (ICEs)	Event	Strategy	Description/Rationale
	ICE 1: Treatment discontinuation in subjects without the use of concomitant rescue therapy or prohibited medication before the planned 24 weeks	Treatment Policy	Observations post ICE are used to reflect clinical practice
Population-level Summary	ICE 2: The use of concomitant rescue therapy or prohibited medication which may impact the efficacy assessment for CC-93538, regardless of treatment discontinuation, before the planned 24 weeks	Composite Variable	Data post ICE will be set as non-responders to reflect treatment failure
	Difference in proportions between treatment groups		

9.6.1.2 *Change in Dysphagia Days (DD) from Baseline to Week 24 (Induction Phase)*

The mean change in dysphagia days (DD), evaluated over the prior 14-day period using the mDSD, from baseline to Week 24 is one of the 2 co-primary endpoints for the Induction Phase.

A DD is defined as a “yes” response to any or all of mDSD questions 2, 3, and 4. In calculating the number of DD for each subject, if the number of measurable diary days (defined as a diary day for which Questions 2 to 4 are answered) over the 14-day period prior to Day 1 is less than 11 or post-Day 1 visits are less than 8, the normalization formula will not be applied and the value of DD will be set to missing. In addition, subjects with at least 8 measurable diary days at post-Day 1 visits that are very unbalanced across the two weeks, defined as less than 3 measurable diary days in either the first or second week, will also have the value of DD set to missing.

The primary analysis will be conducted on the ITT population based on an analysis of covariance (ANCOVA) model with treatment group, Steroid Inadequate Responders/Intolerant status (yes or no), and baseline DD values included in the model. The comparison between CC-93538 360 mg SC once weekly and placebo for change in DD from baseline at Week 24 will be made using the difference in least squares (LS) mean at a 5% 2-sided significance level. Point estimates for the mean difference between the 2 treatment groups using the adjusted LS Mean changes and corresponding 95% Wald CI will be reported. In addition, adjusted LS Means with standard error (SE), arithmetic means with standard deviation (SD), and arithmetic mean changes with SD will be summarized by treatment group.

Missing data will be handled using a multiple imputation (MI) approach ([SAS Institute, 2015](#)) under a missing at random (MAR) assumption.

The following sensitivity analyses will be performed to support the main estimand analysis and provide additional insights to understand the treatment effect:

- Robustness due to missing data MI under MAR assumption will be explored using tipping point analysis ([Yan, 2009](#); [Campbell, 2011](#); [Yuan, 2014](#)).
- A minimum of 4 measurable diary days per week is required to derive a DD score for the 14-day period. The analysis method will be the same as the primary analysis.

In considering the ICEs of study interest (ie, ICE number 2, use of rescue therapy/prohibited medication), supplementary analyses will be performed using the treatment policy estimand strategy and a hypothetical estimand strategy. In addition to the overall population, change in DD from baseline to Week 24 will be analyzed in the Steroid Inadequate Responders/Intolerant subgroup. This analysis will be similar to the overall population except that the ANCOVA model will not include Steroid Inadequate Responders/Intolerant status. See Section [9.6.4](#) for details on the hierarchical testing procedure to control the Type I error rate.

9.6.1.3 *Eosinophilic Histologic Response at Week 24 (Induction Phase)*

The other co-primary endpoint, eosinophilic histologic response, is defined as a peak esophageal eosinophil count $\leq 6/\text{hpf}$ (across all available esophageal levels) at Week 24.

The primary analysis of the eosinophilic histologic response will be conducted on the ITT population using the CMH test at a 2-sided 5% significance level, stratified by Steroid Inadequate Responders/Intolerant status. For treatment comparison between CC-93538 360 mg SC once weekly and placebo, the 2-sided 95% CI for the difference in proportions using the CMH weights and the 2-sided p-value from the CMH test will be provided.

Missing data in subjects without use of rescue therapy/prohibited medication prior to Week 24 will be handled using a multiple imputation (MI) approach ([SAS Institute, 2015](#)) under a missing at random (MAR) assumption.

A sensitivity analysis will be performed using tipping point analysis to assess the robustness of the primary efficacy analysis with regards to handling of missing data.

In considering the ICEs of study interest (ie, ICE number 2, use of rescue therapy or prohibited medication which may impact the efficacy assessment), a supplementary analysis using the treatment policy estimand strategy for the histologic endpoint at Week 24 will be conducted.

In addition to the overall population, histologic response at Week 24 will be analyzed in the Steroid Inadequate Responders/Intolerant subgroup. This analysis will be similar to the overall population except that the analysis will be done using the chi-square test. See Section [9.6.4](#) for details on the hierarchical testing procedure to control the Type I error rate.

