2 STUDY OBJECTIVES AND ENDPOINTS

The objectives for this study are listed in [Table 1](#), and the study endpoints are described in [Table 2](#) for the Induction Phase and [Table 3](#) for the Maintenance Phase.

Table 1: Study Objectives

Primary Objectives
The primary objectives of the study are: 
• To assess the efficacy of CC-93538 versus placebo in reducing dysphagia symptoms at 24 weeks• To assess the efficacy of CC-93538 versus placebo in reducing esophageal eosinophil counts at 24 weeks
Secondary Objectives
The secondary objectives are: 
• To assess the efficacy of CC-93538 versus placebo at 24 weeks in improving:
– Endoscopic features of eosinophilic esophagitis (EoE)– Histologic features of EoE• To assess the persistence of effect of CC-93538 at 48 weeks in reducing:
– Dysphagia symptoms– Esophageal eosinophil counts• To assess the persistence of effect of CC-93538 through administration of a less frequent dosing regimen at 48 weeks in reducing:
– Dysphagia symptoms– Esophageal eosinophil counts

Table 1: **Study Objectives**

• To assess the persistence of effect of CC-93538 at 48 weeks in improving:
– Endoscopic features of EoE– Histologic features of EoE• To evaluate the time to and frequency of EoE flare events and use of rescue therapy during the study• To evaluate the safety and tolerability of CC-93538 including characterization of the immunogenicity profile• To assess trough concentrations of CC-93538 in subjects with EoE

[figure not shown]

Table 2: **Study Endpoints: Induction Phase Endpoints at Week 24**

For endpoints listed below with statistical comparisons, the CC-93538 360 mg SC once weekly treatment arm (2 active arms combined) will be compared to the placebo arm.

Induction Phase Endpoints at Week 24			
Endpoint	Name	Description	Timeframe
Co-primary	Change in DD Clinical Response	The mean change in dysphagia days (DD), evaluated over the prior 14-day period using the modified Daily Symptom Diary (mDSD), from baseline to Week 24	Week 24
	Eosinophil Histologic Response (≤ 6/hpf)	The proportion of subjects with eosinophilic histologic response defined as a peak esophageal eosinophil count ≤ 6/high-power field (hpf) at Week 24	Week 24

Table 2: Study Endpoints: Induction Phase Endpoints at Week 24

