For the fourth key secondary endpoint, mean change in the mean adjusted histology stage score as measured by the scoring system (EoEHSS) from baseline to Week 24, the main analysis will be conducted based on the ITT population using an ANCOVA model with treatment group, Steroid Inadequate Responders/Intolerant status (yes or no), and baseline mean adjusted histology stage score values included in the model. The same summary and inferential statistics will be reported as specified for the primary analysis of the co-primary endpoint of change in DD in Section 9.6.1.2. Missing data and ICEs of interest will be handled via the same strategy as for the primary analysis of the co-primary endpoint of change in DD.

For the fifth key secondary endpoint, mean change in mDSD composite score from baseline to Week 24, the main analysis will be conducted based on the ITT population using an ANCOVA model with treatment group, Steroid Inadequate Responders/Intolerant status (yes or no), and baseline mDSD composite score values included in the model. The same summary and inferential statistics will be reported as specified for the primary analysis of the co-primary endpoint of change in DD in Section 9.6.1.2. Missing data and ICEs of interest will be handled via the same strategy as for the primary analysis of the co-primary endpoint of change in DD.

For the binary endpoint (the first key secondary endpoint), a supplementary analysis using the treatment policy estimand strategy will also be conducted. All observed data will be used regardless of ICE.

For continuous endpoints (second to fifth key secondary endpoints), supplementary analyses using the treatment policy estimand strategy and a hypothetical estimand strategy to handle ICEs of rescue therapy/prohibited medication use will also be conducted. Data will be analyzed using the same ANCOVA model as described in this section.

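### The Week 24 ANCOVA pools one residual variance across a 2:1 comparison, so its standard error is wrong if the arms differ in spread; a robust variance should be pre-specified, although the direction of the error is not established

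*Combined protocol and SAP*

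**What the plan says.** Section 9.6.1.2 analyses change in DD at Week 24 with an "analysis of covariance (ANCOVA) model with treatment group, Steroid Inadequate Responders/Intolerant status (yes or no), and baseline DD values included in the model"; for the LS-mean difference, the "corresponding 95% Wald CI will be reported". The test uses a "two-sided significance level (alpha) of 0.05" (Section 9.3).

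The allocation for this comparison is 2:1. Table 2 in Section 2 says that "the CC-93538 360 mg SC once weekly treatment arm (2 active arms combined) will be compared to the placebo arm", and Section 9.3 gives "266 subjects for CC-93538 and 133 subjects for placebo". Planning uses a single pooled SD of 4.76.

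Under Section 9.6.1.1, data after rescue therapy or relevant prohibited medication (ICE 2) are set to the "worst possible value for change in DD". No number is attached to that value. Section 9.6.2 uses the same form of model for EREFS, EoEHSS grade, EoEHSS stage and the mDSD composite, and says for each that "ICEs of interest will be handled via the same strategy as for the primary analysis of the co-primary endpoint of change in DD". Missing data are multiply imputed.

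The text available for this review names no heteroscedasticity-consistent or arm-specific variance. Section 9.1 defers further detail to the SAP, whose text is not part of what was supplied.

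**The concern.** Ordinary ANCOVA estimates one residual variance and uses it for both arms. With equal arm sizes this does little harm when the variances differ. At 2:1 the larger arm dominates the pooled estimate, while the smaller arm contributes most of the true variance of the difference.

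Two features make unequal variances likely. DD runs from 0 to 14, so an effective treatment compresses active values towards the floor. The worst-value rule also adds a cluster of extreme values to each arm, and the size of each cluster depends on that arm's rescue rate. At stake are the intervals for one co-primary and four key secondary endpoints, all of which sit in the testing hierarchy of Section 9.6.4.

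**Working it through.** **1. The plan's own figure.** With 212 and 106 evaluable, SD 4.76 and difference 2.79 (Section 9.3), SE = 4.76 × √(1/106 + 1/212) = 0.566. Then 2.79/0.566 = 4.93, and power = Φ(4.93 − 1.96) = 99.8%. The stated bound of at least 90% is met.

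**2. The standard error at 2:1.** Take 2n active with variance Va and n placebo with variance Vp.
- True variance of the difference: Va/(2n) + Vp/n = (Va + 2Vp)/(2n).
- Pooled model: [(2Va + Vp)/3] × [1/(2n) + 1/n] = (2Va + Vp)/(2n).
- True SE / model SE = √[(Va + 2Vp)/(2Va + Vp)].

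With VR = Vp/Va, coverage of a nominal 95% interval is 2Φ(1.96/ratio) − 1:

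| VR | SE ratio | Coverage |
|---|---|---|
| 0.8 | 0.964 | 95.8% |
| 1.0 | 1.000 | 95.0% |
| 1.2 | 1.031 | 94.3% |
| 1.5 | 1.069 | 93.3% |
| 2.0 | 1.118 | 92.0% |

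**3. What the worst-value rule does to VR for DD.** Within an arm with rescue proportion p, mean change m and worst change W, variance ≈ (1−p)·4.76² + p·s² + p(1−p)(W−m)², where s is the SD of the worst change. Assumptions: m = −3.00 on placebo and −5.79 on active; baseline mean 9 and SD 3. The worst value is taken either as DD = 14 (W = 5 on average, s = 3) or as a fixed change of +10 (s = 0), which is 14 minus the minimum baseline of 4.

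Example with +10 and rescue of 10% on placebo and 3% on active:
- Vp = 0.9 × 22.66 + 0.09 × 13² = 35.6
- Va = 0.97 × 22.66 + 0.0291 × 15.79² = 29.2
- VR = 1.22, coverage 94.2%

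| Rescue, placebo / active | VR, DD = 14 / +10 | Coverage, DD = 14 / +10 |
|---|---|---|
| 10% / 10% | 0.85 / 0.83 | 95.6% / 95.7% |
| 10% / 5% | 0.98 / 1.07 | 95.1% / 94.7% |
| 10% / 3% | 1.06 / 1.22 | 94.8% / 94.2% |
| 20% / 5% | 1.10 / 1.35 | 94.6% / 93.8% |
| 30% / 5% | 1.16 / 1.54 | 94.4% / 93.2% |

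The worst value lies further from the active mean than from the placebo mean, so each rescued active subject adds more variance. With equal rates the active arm is the noisier one.

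**4. The mDSD composite.** Section 6.4.2.1 gives a range of 0 to 70. Assumptions: baseline 30, so W = +40; SD 12 to 15; mean changes −6.41 and −13.31, borrowed from the Phase 2 DSD composite in Section 1.2.2.7, which used a different version of the diary. The same formula with s = 0 gives:

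| Rescue, placebo / active | VR, SD 12 / SD 15 | Coverage, SD 12 / SD 15 |
|---|---|---|
| 10% / 10% | 0.84 / 0.86 | 95.6% / 95.5% |
| 12% / 8% | 1.04 / 1.02 | 94.9% / 94.9% |
| 10% / 5% | 1.19 / 1.14 | 94.3% / 94.5% |
| 10% / 3% | 1.45 / 1.32 | 93.5% / 93.9% |
| 15% / 3% | 1.79 / 1.55 | 92.6% / 93.2% |

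**5. Check by simulation.** The ANCOVA was fitted at 266/133 with 2,500 runs per scenario (Monte Carlo error about 0.4 points). For DD on the bounded scale with worst DD = 14:
- No rescue: residual VR 1.19, coverage 93.6%, HC3 94.4%. This is the floor effect alone.
- Rescue 10% placebo / 3% active: VR 1.25, coverage 93.6%, HC3 94.8%.
- Rescue 10% in both arms: VR 0.91, coverage 95.3%, HC3 95.2%.

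Over all DD scenarios, including the extreme ones, model-based coverage ran from 92.6% to 96.0% and HC3 from 94.1% to 95.6%. With identical distributions in both arms, model-based coverage was 95.0%. Bounded-scale simulations of the mDSD composite (3,000 runs each) gave 93.2% at 10%/5%, 92.3% at 10%/3% and 91.1% at 15%/3%, with HC3 at 94.5–95.4%.

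**6. Power after correction.** With the largest corrected SE in the 30%/5% case of step 3 (0.801 at 106 against 212), 2.79/0.801 = 3.48, and power = Φ(3.48 − 1.96) = 94%.

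The simulations use complete data. The planned imputation, with 20% dropout, was not modelled.

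**The case against.** The strongest objection concerns direction. A reader might infer that the composite rule makes placebo more variable and that the plan's intervals are therefore too narrow. The documents do not support this. They give no rescue rate by arm, no SD by arm and no numerical worst value. ICE 2 also includes prohibited medication, which need not follow lack of efficacy. Steps 3 and 4 show that equal rescue rates reverse the sign, and that at 10% against 5% the DD variances are about equal. This objection stands. What remains against it is the floor effect, which the formula in step 3 omits, and the expectation that an effective drug reduces rescue. Both point towards placebo, but neither is quantified in the documents.

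A reader might also infer inflated false-positive rates. That is not shown: with the same distribution in both arms the model holds its level. Nor does the 2:1 argument carry over to Week 48, where Section 9.6.3 fits three arms randomised 1:1:1. At VR 1.5, with equal variances in the two active arms, the SE error there is √[2.5/(2 × 3.5/3)] − 1 = 3.5%, against 6.9% at 2:1.

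For EREFS and EoEHSS the supplied text states no score range, so no coverage figure can be derived for them. The supplementary treatment-policy and hypothetical analyses would show whether the assigned worst values drive the result, but they leave the standard error of the main analysis unchanged. The SAP may already settle the matter; the text at hand does not.

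**Conclusion.** The point holds as a conditional one. An ANCOVA with one residual variance in a 2:1 comparison gives a wrong standard error whenever the arm variances differ, and the plan provides no safeguard. Unequal variances are likely here; which arm is noisier is not established.

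The effect is small for DD: coverage of about 94–96% under most assumed inputs, falling to roughly 93% only in harsh cases. For the mDSD composite it is moderate, at about 92–95% when placebo rescue is more frequent, with the low end reached only if placebo rescue is several times the active rate. These figures rest on assumed rescue rates, means, SDs and worst values, and on complete data. The stated power is not undermined, and no confirmatory conclusion is shown to change. The change is worth making because it is nearly free and would look post hoc if chosen after unblinding. Confidence is high for the mechanism and limited for its direction and size.

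**What to change.** In Sections 9.6.1.2 and 9.6.2, and in the Steroid Inadequate Responders/Intolerant (SIR-I) analysis of DD at Week 24, keep the ANCOVA point estimate. State that its standard error will be computed within each imputed data set with a heteroscedasticity-consistent (HC3) variance or with treatment-specific residual variances, and that the results will then be combined by Rubin's rules to give the interval and p-value. The same option may be used at Week 48 for consistency, but the figures above do not justify it there.

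The cost is one sentence in the SAP and one programming option, with no change to data or sample size. Intervals become slightly wider if placebo is the more variable arm and slightly narrower if active is.

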For the co-primary histologic endpoint, eosinophilic histologic response is defined as a peak esophageal eosinophil count $\leq 6/\text{hpf}$, across all available esophageal levels, at Week 24, as this is the threshold recommended in the draft and final FDA guidance for developing drugs for the treatment of EoE (FDA, 2019, FDA, 2020). This threshold is also supported by the report of a retrospective cohort trial utilizing the University of North Carolina EoE Database (Wolf, 2015). The study generated receiver operator characteristic curves for symptom and endoscopic response at different eosinophil count cutpoints (eosinophils/hpf) on 199 patients. The cutpoints examined were < 30 eosinophils/hpf, < 20 eosinophils/hpf, < 15 eosinophils/hpf, < 10 eosinophils/hpf, < 5 eosinophils/hpf, < 3 eosinophils/hpf, ≤ 1 eosinophils/hpf, and 0 eosinophils/hpf. Among patients achieving a similar cut-off of < 5 eosinophils/hpf, 90% had endoscopic response, 86% had clinical response, and 79% had both symptomatic and endoscopic response. Finally, this threshold provides confirmation of significant histologic response as it surpasses the current eosinophil threshold required for the diagnosis of EoE, which is ≥ 15 eosinophils/hpf (Wolf, 2015).

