4.2 Inclusion Criteria

Subjects must satisfy the following criteria to be enrolled in the study:

- 1) Subject must be ≥ 12 years and ≤ 75 years of age and have a body weight of ≥ 40 kg (88.2 lb) at the time of signing the informed consent form (ICF)/assent form.

Note: Countries or sites with local restrictions that prohibit enrollment of adolescents (aged 12 to 17 years inclusive) will only enroll subjects who are 18 years of age or older. Enrollment of adolescent subjects will begin only after the applicable regulatory requirements for enrolling subjects in that age group have been satisfied and the necessary health authority approvals have been granted. Where national or regional guidelines for the definition of adolescence differ from the definition stated above, the national or regional guidelines may be used to determine eligibility. In Austria, Germany, Spain, and Switzerland, adolescent subjects will not be enrolled.

- 2) Subject has histologic evidence of EoE, defined as a peak count of ≥ 15 eosinophils per high-power field (hpf) at any 2 levels of the esophagus (proximal, mid, and/or distal) when off anti-inflammatory therapy (eg, corticosteroids, see Exclusion Criterion 7) for EoE. The histologic criterion for diagnosis of EoE must be confirmed by a centrally read histological assessment of an EGD specimen during the Screening Period prior to randomization.
- 3) Subject has symptoms of dysphagia of at least 4 DD, as assessed with the mDSD instrument, over the last 2 consecutive weeks (14 days) prior to Day 1 when off anti-inflammatory therapy (eg, corticosteroids, see Exclusion Criterion 7) for EoE. Subjects are required to have at least 11 days of diary data out of the final 14-day period of screening mDSD collection in order to be enrolled in the study. During these 11 days, responses to questions 2 through 5 of the mDSD instrument must be complete.

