6.4 Efficacy Assessment

6.4.1 *Esophagogastroduodenoscopy (EGD)*

To ensure quality data and standardization, the same person should perform endoscopic procedures at a study site at each study visit.

The EGD biopsy results for eosinophil counts will be read blinded to treatment allocation at a centralized reading facility. Biopsy specimens will be sent to the centralized reading facility, and with the exception of screening, results of the centrally read eosinophil counts will be blinded to

investigative sites. After randomization, a local histologic assessment of EGD biopsy samples should not be performed, unless required for safety reasons (eg, severe EoE flare, AEs, or incidental findings, etc.). Any incidental findings of potential clinical relevance that are not directly associated with the objectives of the study should be evaluated and handled by the Investigator per the site's standard of care and clinical judgement. More detailed instructions for specimen processing, storage, and shipping will be provided in a separate Study Laboratory Manual.

Endoscopic procedures will be performed as follows:

- EGD will be performed at the time points specified in the Table of Events ([Table 4](#) and [Table 5](#)).
- Biopsies should be obtained from 3 levels, the proximal, mid, and distal esophagus, to maximize the likelihood of meeting histologic eligibility criteria for this study as follows:
 - Distal esophagus (3 to 5 cm above the Z-line [squamo-columnar junction])
 - Proximal esophagus (\approx 15 cm above the Z-line and within 10 cm of the esophageal inlet)
 - Mid esophagus (dependent on subject anatomy as described in the Study Laboratory Manual)
- All subsequent biopsies should be obtained from the same levels as the screening biopsies (ie, all 3 levels) maintaining consistency throughout the study.
- Biopsy samples must be obtained from 2 to 4 separate areas at each level, ideally from the areas with the most prominent visible abnormalities. For example, if 2-bite biopsies are being obtained, a minimum total of 4 biopsy fragments (from 2 separate 2-bite biopsies) would be obtained from each esophageal level.

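### Does scoring Week 24 histologic response on whichever esophageal levels are available, with no stated minimum, call for a change?

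*Combined protocol and SAP*

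**What the plan says.** The response definition appears three times with the same qualifier. Section 1.3.2.1 takes the peak count "across all available esophageal levels, at Week 24". Section 9.6.1.3 repeats this for the 6/hpf co-primary endpoint ("across all available esophageal levels) at Week 24"), and Section 9.6.2 does so for the 15/hpf key secondary endpoint.

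Collection is meant to be complete. Section 6.4.1 states: "All subsequent biopsies should be obtained from the same levels as the screening biopsies (ie, all 3 levels"), with samples from 2 to 4 areas at each level.

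For histology, Section 9.6.1.3 plans multiple imputation and a tipping-point analysis for missing data, and a treatment-policy analysis for rescue or prohibited medication. None of these varies the handling of an incomplete set.

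For dysphagia days, Section 9.6.1.2 sets the score to missing when fewer than 8 of 14 post-Day 1 diary days are measurable. It does the same when the days are unbalanced, "defined as less than 3 measurable diary days in either the first or second week". A sensitivity analysis tightens this: "A minimum of 4 measurable diary days per week is required to derive a DD score for the 14-day period".

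Section 9.1 adds: "Analysis details not explained in the statistical section of the protocol will be provided in the Statistical Analysis Plan (SAP"). The document in hand holds no separate SAP text on biopsy levels.

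**The concern.** The two co-primary endpoints look unevenly specified. A thin diary becomes missing and the threshold is stress-tested, while a thin biopsy set is accepted as it stands. Read literally, one evaluable level at or below 6/hpf is a response. Entry asks for more: at least 15 eosinophils/hpf "at any 2 levels of the esophagus (proximal, mid, and/or distal").

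The error has a fixed direction within a subject, because dropping a level cannot raise a maximum. Such a subject also counts as observed, so neither the imputation nor the tipping-point analysis reaches that value.

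At stake would be some unsupported responses on a co-primary endpoint, on the 15/hpf key secondary endpoint and in the Steroid Inadequate Responders/Intolerant subgroup. Membership of the Week 48 endpoint restricted to Week 24 responders would also be affected. No planned analysis would separate these responses out.

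**Working it through.** **1. The plan's own figure.** Section 9.3 gives 106 placebo and 212 active subjects after dropout, a placebo rate of 0.05, a 15-point difference (so 0.20 on active), and at least 90% power "with a two-sided significance level (alpha) of 0.05".

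- Pooled rate = (106 × 0.05 + 212 × 0.20)/318 = 0.15
- SE under the null = √[0.15 × 0.85 × (1/106 + 1/212)] = 0.0425
- SE under the alternative = √[0.05 × 0.95/106 + 0.20 × 0.80/212] = 0.0347, or about 3.5 points
- Power = Φ[(0.15 − 1.96 × 0.0425)/0.0347] = 97.3%

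The stated bound holds, with room to spare.

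**2. What an incomplete set can do.** Let f be the share of incomplete sets, equal in both arms. Let m_P and m_A be the chance that a true non-responder on placebo or active with an incomplete set looks like a responder. The observed rates are

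- placebo: 0.05 + 0.95 × f × m_P
- active: 0.20 + 0.80 × f × m_A

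The difference therefore changes by f × (0.80 m_A − 0.95 m_P). It grows only if m_A/m_P exceeds 0.95/0.80 = 1.19. The documents give neither f nor m, so everything below is illustration.

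**3. Same m in both arms.** The difference shrinks by f × m × 0.15.

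| f | m | Placebo / active | Difference | Power |
|---|---|---|---|---|
| 5% | 0.3 | 6.4% / 21.2% | 14.8 | 95.3% |
| 10% | 0.3 | 7.9% / 22.4% | 14.6 | 92.9% |
| 10% | 0.5 | 9.8% / 24.0% | 14.3 | 89.1% |
| 20% | 0.5 | 14.5% / 28.0% | 13.5 | 78.4% |

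**4. Latent-normal model, same correlation in both arms.** Treat the three levels as equicorrelated normal variables with correlation ρ. Fix P(all 3 at or below threshold) at 0.05 on placebo and 0.20 on active, then compute the rate with 2 or 1 levels. Bias among affected subjects = (active rate − 0.20) − (placebo rate − 0.05), in points, from unrounded rates.

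| ρ | 2 levels, placebo / active | Bias | 1 level, placebo / active | Bias |
|---|---|---|---|---|
| 0 | 13.6% / 34.2% | +5.6 | 36.8% / 58.5% | +6.6 |
| 0.3 | 10.3% / 30.1% | +4.9 | 26.2% / 50.3% | +9.1 |
| 0.5 | 8.7% / 27.7% | +4.0 | 20.0% / 44.2% | +9.2 |
| 0.8 | 6.8% / 24.2% | +2.4 | 11.7% / 33.5% | +6.8 |

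Multiplying by f gives the overall shift. For 2 levels it is 0.05 to 0.11 points at f = 2% and 0.24 to 0.56 at 10%. For 1 level it is 0.13 to 0.18 at 2% and 0.66 to 0.92 at 10%.

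**5. The sign is not robust.** With ρ = 0.3 on placebo and 0.8 on active, the bias among affected subjects is −1.1 points (2 levels) and −7.7 points (1 level). At f = 10% that is −0.11 and −0.77 overall.

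**6. The obvious alternative.** Counting every incomplete set as non-response gives a difference of 15 × (1 − f): down 0.30, 0.75 and 1.50 points at f = 2%, 5% and 10%. At each of these shares the move is larger than any shift in steps 3 to 5. Where the available-levels rule itself shrinks the difference (steps 3 and 5), both analyses fall on the same side of the 3-level answer, so the pair does not bound it.

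**The case for a change.** The strongest case is that the plan sees the need for a completeness rule on one co-primary endpoint and omits it on the other. That asymmetry is real: the protocol text gives no minimum number of levels and no sensitivity analysis for incomplete sets. The analogy is only partial, though. Dysphagia days are normalized to 14 days when some are missing, so the score needs a minimum denominator. A peak over the levels at hand is not extrapolated.

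Unequal incompleteness is a fair worry. Assuming 10% on active and 5% on placebo, the step 4 model gives +0.3 to +1.0 points with 2 levels and +1.0 to +2.3 with 1 level. Nothing in the documents suggests such an imbalance in a double-blind trial with blinded central reading, but no level count by arm is planned that would show it. The protocol-deviation summary by treatment in Section 9.4 might catch levels never sampled, but not inadequate tissue.

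Power can also drop below 90% in step 3, but only when m is 0.5. In step 4, m for a 2-level set is at most (34.2 − 20)/80 = 18%, and for a 1-level set at most (58.5 − 20)/80 = 48%. Reaching 0.5 would mean that nearly all incomplete sets had a single level with almost unrelated counts between levels.

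**Conclusion.** No change is needed. The rule for an incomplete set is already in the definition: the word available has a purpose only if a level can be absent, and analysts would apply it the same way in both arms. What is missing is supporting detail of the kind Section 9.1 leaves to the SAP.

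Under equal incompleteness of 2% to 10%, the treatment difference moves by less than 1 point in either direction, against a standard error of about 3.5 points. If incompleteness, misclassification and true response rates are all equal, both arms shift together and the type I error is not inflated. Adding a non-response analysis would leave the primary rule intact and would not reliably bound the truth. Reporting evaluable levels by arm at Weeks 24 and 48 is a reasonable courtesy to readers, not a correction.

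This rests on assumed shares of incomplete sets, on incompleteness being similar across arms, and on sites following the 3-level instruction in Section 6.4.1. Incompleteness near 20% with high misclassification, or a clear imbalance between arms, would reopen the question.
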